NIH	National Institutes of Health
NYHA	New York Heart Association
PD	Proportional derivative
PK	Pharmacokinetics
QA	Quality Assurance
QC	Quality Control
RCT	Randomized Controlled/Clinical Trial
SADE	Serious Adverse Device Event
SAE	Serious Adverse Event
SAP	Statistical Analysis Plan
SC	Subcutaneous
SD	Standard Deviation
SGLT2	Sodium Glucose Cotransporter 2
SH	Severe Hypoglycemia
SMBG	Self-Monitoring of Blood Glucose

Acronym	Abbreviation For
T1D	Type 1 Diabetes
TDD	Total Daily Dose
UADE	Unanticipated Adverse Device Effect
UI	User Interface

PROTOCOL SUMMARY

	Description
Title	The Insulin-Only Bionic Pancreas Pivotal Trial: Testing the iLet in Adults and Children with Type 1 Diabetes
Précis	This multi-center randomized control trial (RCT) will compare efficacy and safety endpoints using the insulin-only configuration of the iLet Bionic Pancreas (BP) System versus a control group using CGM during a 13-week study period. Participants may be enrolled initially into a screening protocol and then transfer into the RCT protocol, or they may enter directly into the RCT protocol. At the completion of use of the BP system (end of RCT for BP Group), participants will enter a 2–4 day Transition Phase and be randomly assigned to either transition back to their usual mode of therapy (MDI or pump therapy) based on therapeutic guidance from the iLet BP System or transition back to their usual mode of therapy based on what their own insulin regimens were prior to enrolling in the RCT.
Investigational Device	iLet Bionic Pancreas System, which consists of an integrated infusion pump, touchscreen display, Bluetooth radio, and insulin dosing algorithms, that automatically controls insulin delivery based on glucose values obtained by communicating with a Dexcom G6 sensor.
Objectives	
Primary Objective
 
 • To compare the efficacy and safety of the insulin-only configuration of the iLet BP System using insulin lispro, insulin aspart, and Fiasp (adults only) in maintaining near-normal glycemia relative to usual care in a home-use study in adults and children with T1D. 
Secondary Objectives
 
 • To assess the impact of the insulin-only configuration of the iLet BP System on quality of life and treatment satisfaction.
Study Design	Randomized clinical trial followed by a Transition Phase for those using the iLet BP System
Number of Sites	~16

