**Date: December 9, 2021**

## Revision History

The following table outlines changes made to the Statistical Analysis Plan.

Version Number	Author	Senior Statistician	Effective Date	Study Stage
1.0	[name]	[name]	December 18, 2020	Pre-randomization.
2.0	[name]	[name]	March 19, 2021	Enrollment.
3.0	[name]	[name]	May 25, 2021	Enrollment.
4.0	[name]	[name]	December 9, 2021	Enrollment completed. Changes made before unblinding of results to study investigators

Version Number	Revision Description
1.0	Original version
2.0	
 
- Removed requirement of baseline data to be 60 days prior to randomization.
 
- Added sub-analyses excluding participants using closed loop systems at baseline.
 
- Updated per-protocol CGM wear requirements for Control group
 

3.0	
 
- Added sensitivity analyses for participants not randomized due to protocol deviation
 
- Added sub-analyses for participants with HbA1c >7.0%
 
- Account for lab HbA1c measurements measured at alternate labs
 
- Added analysis restricting to periods of iLet use only for participants who discontinued iLet use but continued in the study.
 

4.0	
 
- Added statistical tests for site effects.
 
- Clarified subgroup analyses by different age cohorts
 
- Added additional clarification on which outcomes will have confidence intervals.
 
- Revised non-CL cohort at baseline sub-analyses.
 
- Moved transition phase analyses, BP aspart/lispro vs. SC comparison, and BP Fiasp vs. BP aspart/lispro comparisons to separate SAPs.
 
- Removed condition to combine the BP aspart/lispro and BP Fiasp groups; the BP groups will be analyzed separately.
 
- Added additional CGM-measured hyperglycemic event definition.
 

	

- Added safety analyses for pediatric cohort

- Added baseline SH/DKA covariate to SH/DKA safety analyses.

--	---

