15    of an insulin-only configuration of the iLet Bionic Pancreas (BP) system versus a Control group  
16    using CGM during a 13-week study period.

17    The sample size is expected to include ~220 in the BP Group (using aspart/lispro) and ~110 in  
18    the Standard Care Control Group with 50% adults and 50% pediatric participants.

19    Following the initial screening visit, there will be the following visits:

20       a) Randomization Visit  
21       b) Day 1-2 Phone Call  
22       c) Week 1 Phone Call  
23       d) Week 2 Visit  
24       e) Week 6 Visit  
25       f) Week 10 Visit  
26       g) Week 13 Visit

27  
28    **4. Statistical Hypotheses**

29    The primary outcome is:

30       • Superiority in HbA1c at 13 weeks

32 Only the primary outcome needs to be met to declare device efficacy. The key secondary  
33 outcome is:

34 • Non-inferiority in CGM-measured time <54 mg/dL calculated over 13 weeks

35  
36 Primary and key secondary outcome analyses will combine pediatric and adult participants into a  
37 single analysis. The study hypotheses can be stated as follows:

38  
39 HbA1c Outcome:

40 • *Null Hypothesis:* There is no difference in the mean HbA1c at 13 weeks between BP  
41 aspart/lispro and Control Group  
42 • *Alternative Hypothesis:* There is a nonzero difference in the mean HbA1c at 13 weeks  
43 between BP aspart/lispro and Control Group

44  
45 Time <54 mg/dL Outcome:

46 • *Null Hypothesis:* There is a mean difference of at least 1% in the percentage of time spent  
47 with a sensor glucose level below 54 mg/dL between the BP aspart/lispro and Control  
48 Group over the 13 weeks  
49 • *Alternative Hypothesis:* There is a mean difference of less than 1% in the percentage of  
50 time spent with a sensor glucose level below 54 mg/dL between the BP aspart/lispro and  
51 Control Group over the 13 weeks

52  
53  
54 

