## 5. Sample Size

55 The sample size of 440 for the RCT was selected to provide sufficient exposure to the iLet BP  
56 system for regulatory purposes, with respect to different age groups and for use of both insulin  
57 aspart/lispro and Fiasp. RCT completion is expected for 200 participants randomized to BP  
58 aspart/lispro Group and 100 to the Control Group.

59  
60 The primary and key secondary analyses for BP aspart/lispro vs. Control will include both the  
61 pediatric and adult participants in a single analysis. Superiority for HbA1c at 13 weeks and non-  
62 inferiority for time <54 mg/dL measured with CGM at intervals over the 13 weeks are  
63 considered the primary and key secondary endpoints, respectively. Statistical power for each  
64 endpoint was computed assuming the following:

65 • HbA1c: Statistical power is >99%, assuming true mean HbA1c difference of 0.4% between  
66 BP aspart/lispro and Control Group, standard deviation of 13-week HbA1c of 0.8%,  
67 correlation between baseline and 13-week HbA1c of 0.40, two-sided type 1 error of 5%

68 • Time <54 mg/dL: Statistical power is 99%, assuming no true difference in mean time <54  
69 mg/dL between BP aspart/lispro and Control Group, a non-inferiority margin of 1%, standard  
70 deviation of percent time <54 mg/dL of 2.0%, correlation between baseline and follow-up of  
71 0.40, and one-sided type 1 error of 0.025%

72  
73 A separate document details the justification of these power calculations.  
74

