408 further detailed in Section 7.1.

409

410 Formal statistical testing only will be performed for selected safety endpoints. For the following  
411 outcomes, mean and standard deviation (SD) or summary statistics appropriate to the distribution  
412 will be tabulated by treatment group and formal statistical comparisons will be performed if there  
413 are enough events (at least 5 events combined between the BP aspart/lispro and Control Group):

- 414 • Number of SH events and SH event rate per 100 person-years
- 415 • Number of DKA events and DKA event rate per 100 person-years
- 416 • Other serious adverse events
- 417 • Worsening of HbA1c from baseline to 13 weeks by >0.5%

418

419 If enough events occur for the severe hypoglycemia (SH), DKA, and other serious adverse event  
420 (SAE) outcomes, the numbers of events will be compared between the two treatment groups  
421 during the RCT using a Poisson regression model adjusting for baseline age and HbA1c, and site  
422 as a random effect. For SH, the model will additionally control for whether or not the participant  
423 experienced at least 1 SH event prior to randomization. For DKA, the model will additionally  
424 control for whether or not the participant experienced at least 1 DKA event prior to  
425 randomization. If distribution is zero-inflated or the variance is greater than its mean, then a  
426 zero-inflated Poisson or negative binomial regression model will be considered. For worsening  
427 of HbA1c from baseline to 13 weeks by >0.5%, a logistic regression model adjusting for baseline  
428 age and HbA1c and site as a random effect will be used to compare the two treatment groups.

429

430 Since the Control Group is not provided with a study blood glucose meter or blood ketone meter,  
431 no treatment group comparisons of meter data will be performed. Additionally, no formal  
432 statistical comparison will be made of all reported adverse events combined since there are

433 specific requirements in the protocol for reporting certain events in real-time for the BP Group  
434 but not the Control Group, and adverse device effects are only reported for the BP Group.

435

436 No adjustments for multiple comparisons will be made for any safety analyses.

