## 587 **16. Additional Exploratory Analyses**

588 Additional analyses comparing treatment groups will include:

589

590     • \*\*\*Comparison of aspart/lispro BP Group versus Control Group in adults  $\geq 18$  years old  
591        and separately for participants  $< 18$  years old for the safety outcomes described for the  
592        main RCT analyses. *p*-values will be produced using similar models as detailed in  
593        Section 10.

594

595     • Separate CGM analyses for daytime and nighttime. The following CGM metrics will be  
596        tabulated separately for daytime and nighttime by period (i.e. baseline and follow-up),  
597        and also by 4-week follow-up periods:  
598        ○ Mean glucose  
599        ○ Glucose SD  
600        ○ Glucose coefficient of variation  
601        ○ % time in range 70-180 mg/dL  
602        ○ % time above 180 mg/dL  
603        ○ % time above 250 mg/dL  
604        ○ % time below 70 mg/dL  
605        ○ % time below 54 mg/dL

605

For the time-of-day analyses, at least 126 hours of daytime CGM data and at least 42 hours of nighttime CGM data will be required. Boxplots of % time 70-180 mg/dL and % time <54 mg/dL by time of day and by 4-week period will be produced.

606

607     ●    \*\*\*Intersubject variability of HbA1c

608

609     **16.1 Other Analyses, Tabulations, and Figures**

610

611     ●    \*\*\*Scatterplots of HbA1c and % time 70-180 mg/dL vs. CGM and closed loop use and  
612        change in HbA1c and time 70-180 mg/dL versus CGM and closed loop use.

613

614

**IOBP Pivotal Trial  
Statistical Analysis Plan  
BP Fiasp**

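### No confidence interval is specified for the between-arm comparison of severe hypoglycemia, DKA or other serious adverse events, so the plan does not report how large an excess remains compatible with the data

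*SAP*

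**What the plan says.** Safety is part of the primary objective. The Protocol Summary begins it: "To compare the efficacy and safety of the insulin-only configuration of the iLet BP System". SH, DKA and other SAEs are the listed key safety outcomes.

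SAP Section 10 provides that the safety summaries "will be tabulated by treatment group and formal statistical comparisons will be performed if there" "are enough events (at least 5 events combined between the BP aspart/lispro and Control Group". The summaries for SH and DKA are the number of events and the rate per 100 person-years. When the gate is passed, arms are compared by a Poisson regression adjusted for age, HbA1c and site (random), plus prior SH or prior DKA for those two outcomes. Zero-inflated or negative binomial models are the fallback. All p-values are two-sided (Section 8.1), and safety tests carry no multiplicity adjustment.

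Section 16 repeats the safety comparison in adults and in children: p-values "will be produced using similar models as detailed in" Section 10. Section 14 also describes the safety output as p-values. The Fiasp SAP (Section 6) takes over the same safety analyses, in adults only.

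Elsewhere 95% intervals are assigned outcome by outcome: HbA1c (9.1), time <54 mg/dL (9.2), continuous CGM metrics and binary secondary outcomes (9.3), all hierarchical outcomes (9.4), total daily insulin, weight and BMI (9.6) and the sub-analyses (13.1). The entry for version 4.0 in the revision history reads "Added additional clarification on which outcomes will have confidence intervals". Sections 10 and 16 name none for safety.

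**The concern.** SH and DKA are rare, the trial is short, and its size was set by device exposure for regulatory purposes and not by the ability to compare these events. In that setting a test mostly returns a non-significant p-value, and the useful quantity is the range of rate ratios that the data leave open. The plan assigns that range to body weight and BMI but not to SH or DKA.

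Followed as written, the between-arm inference on the key safety outcomes is a p-value at 5 or more combined events and nothing below that. A reader of p>0.05 would see two rates, but no planned statement of whether a doubling or tripling on BP is still compatible with the data.

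**Working it through.** **Inputs.** SAP Section 3: "The sample size is expected to include ~220 in the BP Group (using aspart/lispro) and ~110 in" Control, "using CGM during a 13-week study period". Section 10 analyses all randomized participants, so the randomized numbers are used. SAP Section 5 gives the completers: "RCT completion is expected for 200 participants randomized to BP" aspart/lispro, and 100 in Control. The gate is 5 combined events. The alpha for safety tests is not stated; 5% two-sided is assumed. No Control rate for SH or DKA is given, so a range is shown.

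**The plan's own power first.** SAP Section 5, 200 vs 100, correlation 0.40:
- HbA1c: SE = 0.8 × √(1 − 0.40²) × √(1/200 + 1/100) = 0.0898. 0.4/0.0898 = 4.45. Power = Φ(4.45 − 1.96) = 99.4%.
- Time <54 mg/dL: SE = 2.0 × √(1 − 0.40²) × √(1/200 + 1/100) = 0.2245. 1/0.2245 = 4.45. Power = 99.4%.

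The stated >99% and 99% reproduce. No corresponding figure is given for SH or DKA.

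**Exposure.** BP: 220 × 91/365.25 = 54.8 person-years. Control: 110 × 91/365.25 = 27.4. These assume full follow-up.

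**Chance of missing a true doubling on BP.** The two counts are taken as independent Poisson, with Control mean r × 27.4 and BP mean 2r × 54.8. All pairs of counts are enumerated. A pair counts as detection if the total is at least 5, two-sided p<0.05, and the BP rate is the higher. The exact test conditions on the total, with null BP share 54.8/(54.8 + 27.4) = 2/3, and doubles the smaller tail.

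| Control rate per 100 PY | Expected events, BP / Control | P(fewer than 5 events) | Missed, likelihood-ratio | Missed, exact conditional |
|---|---|---|---|---|
| 2 | 2.2 / 0.5 | 86% | 95.9% | 100% |
| 5 | 5.5 / 1.4 | 19% | 82.9% | 98.6% |
| 10 | 11.0 / 2.7 | 0.2% | 80.0% | 90.5% |
| 20 | 21.9 / 5.5 | <0.1% | 66.4% | 75.4% |
| 30 | 32.9 / 8.2 | <0.1% | 51.4% | 60.5% |
| 40 | 43.9 / 11.0 | <0.1% | 39.1% | 47.0% |
| 60 | 65.8 / 16.4 | <0.1% | 21.9% | 26.6% |

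With half the exposure (adults only, children only, or Fiasp vs adult Control; about 27.4 vs 13.7 person-years), the likelihood-ratio / exact miss rates are 93/100% at 5, 83/99% at 10, 80/91% at 20 and 73/83% at 30 per 100 person-years.

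**What an interval would show.** Let L and U be the Clopper-Pearson limits for the BP share of events. The rate-ratio limits are L/(1 − L) × 27.4/54.8 and U/(1 − U) × 27.4/54.8; the exposure ratio is 1/2.
- 10 BP vs 5 Control (ratio 1.0): share limits 0.384 and 0.882, so the 95% CI is 0.31 to 3.7, with p = 1.0.
- 12 vs 3 (ratio 2.0): share limits 0.519 and 0.957, so the CI is 0.54 to 11, with p about 0.42.
- 4 vs 2 (ratio 1.0): share limits 0.223 and 0.957, so the CI is 0.14 to 11.1.
- No BP events in 54.8 person-years: the upper limit of the two-sided 95% interval is −ln(0.025)/54.8 = 3.69/54.8, or 6.7 per 100 person-years.

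In the first two cases p is well above 0.05 while a tripling remains inside the interval.

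**The case against.** Several points against this are fair.

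- **Counts and rates by arm are tabulated and each event is listed.** Point estimates will be visible, and a reader could derive an unadjusted interval, as above. That stands. It would be wrong to infer that the plan yields nothing beyond a verdict of significance; what it lacks is a planned statement of uncertainty.
- **A Poisson model yields a rate ratio and interval as routine output, and silence does not forbid reporting it.** True, but nothing commits to it, and elsewhere the SAP names its intervals. One might infer from the version 4.0 entry that safety was deliberately left out. The entry lists no outcomes and does not show that.
- **Nothing says that a non-significant result will be taken as evidence of safety.** Correct. Only HbA1c decides efficacy, no pass/fail rule attaches to SH or DKA, and the Medical Monitor and DSMB review each such event. The misreading is possible and unguarded, but it is not planned.
- **Hypoglycemia has an inferential comparison with an interval.** Time <54 mg/dL has a 95% CI and a 1% margin. This is relevant, but it does not cover SH as a clinical event, DKA or other SAEs.
- **The miss rates are not properties of the trial.** They rest on an assumed Control rate, and the tests above are unadjusted stand-ins for the planned covariate-adjusted mixed model. This stands, so no single figure should be quoted without its rate and test.
- **The age-group p-values in Section 16 are exploratory** and marked as not intended for the primary manuscript. This lowers their weight but leaves Section 10 unchanged.

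**Conclusion.** The point holds as a gap in planned reporting. For SH, DKA and other SAEs the plan gives counts and rates by arm (listings for each event), a p-value at 5 or more combined events, and no between-arm inference below that. It specifies no interval at any count.

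The p-value alone says little about a doubling over much of the plausible range. The miss rate is about 51% to 83% (likelihood-ratio) or 61% to 99% (exact conditional) for Control rates of 30 down to 5 per 100 person-years, about 22% to 27% at 60, and near 100% at 2. These figures assume 220 vs 110 participants followed for 91 days, Poisson counts, and a 5% two-sided test. Overdispersion would raise them.

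Low power for rare events is not itself an error here, since the size was chosen for exposure. It is the reason why an interval should be the planned output. The documents also do not support requiring the safety conclusion to rest on the upper confidence limit: no margin for SH or DKA is set against which to judge it. This is a cheap improvement and does not affect the efficacy analyses.

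**What to change.** In SAP Sections 10 and 16, and so through the Fiasp SAP:

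1. Report for SH, DKA and other SAEs the between-arm rate ratio and/or rate difference with a 95% CI, whatever the number of events. Use exact or profile-likelihood limits when counts are small.
2. When an arm has no events, add a one-sample upper bound for the BP rate.
3. Keep the p-value as a supplement under the existing 5-event rule, and state that p>0.05 is not evidence of no excess.

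No margin or new decision rule is needed. The cost is SAP wording and a few table columns, with no new data and no effect on alpha. The drawback is that the intervals will be wide and look less reassuring than a p-value alone.

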### 437 **10.1 Safety Tabulations Specific to the BP Group**

438 For the BP group, the following will be tabulated :

439     • Adverse device effects (ADE)  
440     • Serious adverse device events (SADE)  
441     • Unanticipated adverse device effects (UADE)

442

## 443 **11. Additional Tabulations and Analyses**

444 The following tabulations will be performed according to treatment group:

445     • Baseline demographics and clinical characteristics  
446     • A flow chart accounting for all participants for all visits  
447     • Visit completion rates for each follow-up visit  
448     • Protocol deviations  
449     • Modifications in insulin delivery type in the Control Group (e.g. change between  
450       MDI/CSII) during the study  
451     • Number and reasons for unscheduled visits and phone calls  
452     • CGM usage

### 453 **11.1 Tabulations Specific to the BP Group**

454 The following will be tabulated in the BP group:

455     • Number of participants who stopped BP use and reasons  
456     • % time in closed loop  
457     • % CGM capture while iLet is on  
458     • % time device was autonomously dosing while iLet is on  
459     • Total daily insulin dose by week during the first month and then by month, and also  
460       according to baseline HbA1c  
461     • Participant completed surveys specific to BP Group  
462     • Device malfunctions requiring study team contact and other reported device issues

### 463 **11.2 Baseline Descriptive Statistics**

464 Baseline demographic and clinical characteristics of the study cohort will be summarized. The  
465 following descriptive statistics will be tabulated overall and by randomization group:

466     • Age in years at randomization  
467     • Gender  
468     • Race  
469     • Ethnicity  
470     • Type I diabetes duration in years at randomization  
471     • BMI (if available and participant is  $\geq 18$  yr)  
472     • BMI percentile (if available and participant is  $< 18$  yr)  
473     • HbA1c (% mmol/L)  
474     • C-peptide  
475     • Current insulin modality  
476     • Past amount of pump use for patients using pump at enrollment  
477     • Daily insulin units  
478     • CGM use status at enrollment  
479     • Time range of most recent severe hypoglycemic event  
480     • Number of severe hypoglycemic events in the last 12 months  
481     • Number of severe hypoglycemic events involving seizure/coma over lifetime  
482     • Number of severe hypoglycemic events involving seizure/coma in the last 12 months  
483     • Time range of most recent DKA event  
484     • Number of DKA events in the last 12 months  
485     • Number of glucose tests per day  
486     • Other non-insulin blood sugar control medications taken

487  
488 For continuous variables, summary statistics appropriate to the distribution will be given. For  
489 discrete variables, number and percentage will be reported for each category. For participants  
490 who have multiple screening visits due to an extended period between initial screening and  
491 randomization, the baseline data closest to randomization will be used.

492  
493 **12. Planned Interim Analyses**

494 No formal interim efficacy analyses are planned as study recruitment is expected to be rapid and  
495 the duration of follow up short. The DSMB will review safety data at intervals, with no formal  
496 stopping rules other than the guidelines provided in the participant-level and study-level stopping  
497 criteria detailed in the protocol.

498  
499 Upon completion of the RCT, the efficacy and safety analyses will be performed in preparation  
500 for PMA submission.

501

